**Randomization.** We used the Sealed Envelope™ program (Sealed Envelope Ltd., 2016) to generate a randomization table to condition (1:1 allocation ratio) using a permuted block design with block sizes of two and four to maximize the likelihood of a balanced sample size across arms (Schulz & Grimes, 2002), and stratifying by rural status to facilitate exploratory analyses of the impact of this variable on trial outcomes and to maximize the likelihood of balance across arms on this potential characteristic (Kernan et al., 1999). We defined rural status as living more than 40 miles away from the closest VA medical facility, in line with eligibility criteria used by the Veterans Access, Choice, and Accountability Act and shown to be a marker indicating decreased likelihood of receiving psychotherapy (Pfeiffer et al., 2010).

**DESTRESS-WV intervention.** For the DESTRESS-WV condition, the initial telephone session with the study coach served to 1) provide brief psychoeducation regarding PTSD; 2) complete a safety plan that is individualized to the patient for times when she is distressed; 3) introduce the intervention model, the study coach role, and the participant's role; 4) introduce the patient to the website's structure; and 5) problem-solve any obstacles to using the website. Participants were asked to log on the website twice a week each week for eight weeks and complete different homework activities. Nonetheless, up to 12 weeks of access was provided. The coach called the participants once a week at an agreed upon time while they were completing the program to monitor symptoms and safety, review progress through the website, provide encouragement, review a particular skill or strategy when applicable, review barriers to treatment compliance, and address barriers to treatment (target call time is 15 minutes). The coach had access to a back-end of the DESTRESS-WV website where she monitored participants' progress, and this was monitored weekly between every study coach call.

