***Process outcomes.*** Feasibility of DESTRESS-WV was examined by completion of intervention sessions and retention of participants through the duration of the intervention. For the DESTRESS-WV treatment arm, we defined a “treatment completer” as someone who completed at least nine of the 16 intervention sessions, and for the phone monitoring only arm we defined a treatment completer as someone who completes at least five of the nine coaching calls. We hypothesized that no more than 30% of the women in this study will dropout from the study (withdraw or be lost-to-follow-up), similar to overall dropout rates for PTSD trials (Imel et al., 2013). Of the women who do not dropout, we hypothesized that at least 70% will be treatment completers as per the above definitions, similar to participation rates found by Engel et al. (2015).

Acceptability was evaluated by participants in both study groups using the Client Satisfaction Questionnaire-8 (CSQ-8; Larsen et al., 1979), an 8-item measure on a 4-point Likert scale that assesses general satisfaction with treatment. For example, participants rate the quality of the service they received, the extent to which the program met their needs, the extent to which they were satisfied with the amount of help received, and whether services helped them deal more effectively with their problems. The measure has good internal consistency, construct validity, and criterion-related validity (Attkisson & Zwick, 1982). An additional item assessed how satisfied participants were with receiving treatment through the phone or Internet (based on assigned condition), from 0 (*not at all*) to 4 (*very much*). Finally, seven items created for the study assessed satisfaction with the study coach, ranging from 0 (*not at all*) to 4 (*very much*). Items included how much the participant liked the coach, how helpful the coach was, and how

much the participant felt the coach listened and understood them. We hypothesized that overall mean satisfaction will be greater than the mid-point of the scale.

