All participants who withdrew from the treatment protocol were given the option of continuing to provide information at the follow-up assessments for intent-to-treat analyses of outcomes. Additionally, participants randomized to DESTRESS-WV were reminded of the study office phone number and the Veterans Crisis Line during each logon. Participants were also reminded of these phone numbers and other resources after each follow-up assessment.

**Power.** This is a pilot RCT designed to provide estimates of feasibility of the treatment approach, dropout rates, acceptability, and initial effect sizes. The study's budget and timeline allows us to plan to randomize 100 participants. For the primary outcome, Litz et al. (2007) observed a differential effect size of 0.41 at 8 weeks ( $n = 33$ ), 0.10 at 3 months ( $n = 24$ ), and 0.95 at 6 months ( $n = 18$ ) when comparing change from baseline in PTSD symptoms for participants randomized to DESTRESS ( $n = 24$ ) versus supportive counseling ( $n = 21$ ), with an overall dropout rate of 27% prior to the end of 8 weeks of therapy. In a second trial of DESTRESS by Engel et al. (2015) where participants were randomized to optimized usual care ( $n = 37$ ) or DESTRESS ( $n = 43$ ), the 6-week effect size was 0.23 ( $n = 64$ ), the 12-week effect size was 0.47 ( $n = 62$ ), and the 18-week effect size was 0.08 ( $n = 66$ ), with an overall dropout rate of 18%.

As noted above, we hypothesized no more than 30% of participants will dropout prior to the end of the study. Thus, with the goal of randomizing 100 participants and assuming a sample size of at least  $n = 35$  participants per group, we have 80% power to detect an effect size of 0.68 using a two-sided Type I error rate of 5%.

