Following the recommendation of Bacchetti (2010), Table 1 presents a sensitivity analysis of possible results from this study in terms of 95% confidence intervals for the difference in change from baseline in PCL-5 for the DESTRESS-WV versus the phone monitoring only group. Engel et al. (2015) state that for their study of DESTRESS versus optimized usual care (OUC), for PCL-4 the observed 12-week change from baseline (Mean  $\pm$  SD) was  $12.6 \pm 16.6$  for the DESTRESS group and  $5.7 \pm 12.5$  for the OUC group. In our table the pooled standard deviation of change from baseline varies from 8 to 22, while the possible difference in change from baseline between groups varies from 0 to 14. The numbers in parentheses after the confidence intervals are the effect sizes.

**Table 1.** Sensitivity Analysis of Possible Results for Difference in Change from Baseline Between Groups (95% Confidence Intervals and Effect Sizes)

	Difference = 14	Difference = 7	Difference = 0
SD = 8	[10.2, 17.8] (1.8)	[ 3.2, 10.8] (0.9)	[ -3.8, 3.8] (0)
SD = 15	[ 6.8, 21.2] (0.9)	[-0.2, 14.2] (0.5)	[ -7.2, 7.2] (0)
SD = 22	[ 3.5, 24.5] (0.6)	[-3.5, 17.5] (0.3)	[-10.5, 10.5] (0)

**RCT data analytic strategy.** We used summary statistics (e.g., means, standard deviations, percentages) and graphs (e.g., strip charts, box plots, bar charts, scatter plots) to compare participant demographics at baseline by assigned treatment group (DESTRESS-WV vs. phone monitoring only), and to initially compare outcomes by treatment group. Analyses followed the intent-to-treat principle, so that all participants who had at least a baseline assessment and were randomized were included in the analyses. For descriptive purposes, analyses were conducted to determine group comparability on baseline participant characteristics and potential moderator variables. Because differential attrition can compromise inference about treatment effectiveness, we compared study dropouts versus non-dropouts and treatment non-completers versus treatment completers on demographic and outcome variables. Dropouts

included those who withdrew from the study or were lost-to-follow-up; treatment non-completers may or may not be study dropouts as treatment non-completers were invited to continue participating in study assessments. Treatment completers include those completing nine or more sessions of DESTRESS-WV or, for those in the phone monitoring condition, five of the nine coaching calls.

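### Does the 30% dropout limit carry two different time windows, so that the same data could meet it or miss it?

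*Combined protocol and SAP*

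**What the plan says.** Four places in the combined protocol and SAP bear on the point.

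- **Process outcomes, the measure.** "Feasibility of DESTRESS-WV was examined by completion of intervention sessions and retention of participants through the duration of the intervention".
- **Process outcomes, the hypotheses.** At most 30% of the women are expected to drop out of the study, by withdrawal or loss to follow-up. This is tied to overall dropout in PTSD trials. Then: "Of the women who do not dropout, we hypothesized that at least 70% will be treatment completers".
- **Power.** "As noted above, we hypothesized no more than 30% of participants will dropout prior to the end of the study". From this the plan assumes at least 35 per group and an effect size of 0.68 at 80% power. The total was not derived from the limit: "The study's budget and timeline allows us to plan to randomize 100 participants".
- **RCT data analytic strategy.** Dropouts "included those who withdrew from the study or were lost-to-follow-up", and they are kept distinct from treatment non-completers, who may stay in follow-up. The mixed-model paragraphs list four PCL-5 assessments over the course of the study, the last at 6 months post-treatment. They also provide for comparing the rate and timing of dropout between groups.

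**The concern.** Process outcomes opens with retention over the intervention and then gives a single retention threshold, so a reader may judge the 30% at the end of treatment. A reader of the Power section would judge it at the end of the study. A woman who answers the 8-week survey and then stops is retained on the first reading and a dropout on the second.

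The Power section adds to the unease. The first cited DESTRESS trial is quoted "with an overall dropout rate of 27% prior to the end of 8 weeks of therapy", beside a limit that runs to the end of the study.

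Feasibility and dropout head the list of purposes of this pilot. If the window were open, the report could declare the dropout hypothesis met or missed from the same data. The 70% completer hypothesis could shift too, because its denominator is the women who have not dropped out. The 35 per group would also lack a visit to which it applies.

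**Working it through.** **1. The plan's own figures.** Inputs from Power and Randomization: 100 randomized 1:1, 30% loss, two-sided 5% level, effect size 0.68.

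- Evaluable per group: 100 × (1 − 0.30) / 2 = 35.
- Two-sample t-test: noncentrality 0.68 × √(35/2) = 2.845, with 68 degrees of freedom and critical value 1.995. Power = 0.801. The effect detectable at 80% power is 0.679.
- Table 1 half-width = 1.995 × SD × √(2/35). SD 8 gives 3.8, SD 15 gives 7.2 and SD 22 gives 10.5. All match.

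**2. Which window goes with which statement.**

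| Place | Statement | Window |
|---|---|---|
| Process outcomes, first sentence | descriptive retention measure | the intervention |
| Process outcomes, 30% hypothesis | dropout from the study | the study |
| Power | the same 30%, by back-reference | to the end of the study |
| RCT data analytic strategy | definition of dropout | withdrawal from the study or loss to follow-up |

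The three rows about dropout agree. Only the retention measure uses the intervention window, and no threshold is attached to it. With the last assessment at 6 months post-treatment, the end of the study can be read from the document.

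**3. Could the window matter in practice?** Loss = 1 − n / randomized, taking the n beside each effect size in the Power section as women or men assessed at that visit. This is an inference, supported by two matches: 12/45 = 26.7% against the stated 27%, and 14/80 = 17.5% against the stated 18%. The last column is the binomial chance of 30 or fewer dropouts among 100.

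| Cited trial | Visit | Loss | P(≤ 30 of 100) |
|---|---|---|---|
| First (45 randomized) | 8 weeks | 12/45 = 26.7% | 81% |
| | 3 months | 21/45 = 46.7% | 0.05% |
| | 6 months | 27/45 = 60.0% | < 0.01% |
| Second (80 randomized) | 6 weeks | 16/80 = 20.0% | 99% |
| | 12 weeks | 18/80 = 22.5% | 97% |
| | 18 weeks | 14/80 = 17.5% | 99.9% |

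The window decides the verdict under the first trial's pattern and is irrelevant under the second's. Even under the first, the plan's stated window gives one answer: the hypothesis would be missed.

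**4. The completer hypothesis.** Suppose 73 non-dropouts at end of treatment, 45 of them completers: 45/73 = 62%, below 70%. To reach 32/40 = 80% at 6 months, 13 of 45 completers (29%) but 20 of 28 non-completers (71%) must leave after treatment. With equal later loss, 45 × 40/73 = 24.7 completers remain among 40, still 62%. A reversal therefore needs strongly unequal later loss, and the documents give no figure for that.

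**5. Does the unlabelled visit harm the power statement?** If at least 35 per group remain at the end of the study and loss is monotone, at least 35 remain at every earlier visit, so the statement holds at each. With 50 randomized per arm, the planned mixed model and an assumed intraclass correlation of 0.3 to 0.8, 6-month power at 0.68 is 81% to 85% when 30% are lost by the end of the study. It falls to 61% to 66% only if 30% are lost by 8 weeks and later loss follows the first cited trial, which is not the plan's assumption.

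**The case for a change.** The best case for a change is that the opening sentence of Process outcomes frames the whole paragraph. The 30% is the only number against which intervention-period retention could be judged, so someone writing the feasibility results could apply it at end of treatment in good faith. The first cited trial shows that this could turn a miss into a success. Naming a visit would cost one sentence, and the planned comparison of dropout timing does not itself say which time decides the hypothesis.

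Part of this stands. The intervention-period retention measure has no threshold of its own. No rule says how to count a woman who misses one survey and answers a later one, and this does happen: the second cited trial's n rises from 62 to 66. The 27% benchmark covers a shorter period than the limit beside it, although the plan rests the 30% on PTSD trials generally.

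The rest does not stand. Judging the 30% at end of treatment means overriding the one place where the plan gives it an explicit end point. The remaining gaps have obvious fillings. A woman who answers the last survey has not been lost to follow-up, and retention over the intervention can be reported as a descriptive percentage beside end-of-study dropout.

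**Conclusion.** No change is needed. The 30% limit has one window, to the end of the study, and its two statements are consistent. The 35 per group, the 80% power at 0.68 and Table 1 are correct under that reading. The total of 100 was set by budget and timeline, so a different window would not alter it.

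What remains is missing detail: no threshold for the intervention-period measure, no rule for intermittent surveys and no visit label on the power contrast. The 30% and 70% are hypotheses in a pilot meant to yield estimates, and no progression or stopping rule depends on them. The rate and timing of dropout are to be compared in any case, so later losses would be examined.

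This conclusion takes the end of the study to be the 6-month post-treatment assessment, as the listed schedule implies. The size of the possible reversal (27% against 60% loss) rests on later rates inferred from one trial of 45 participants. The other cited trial, with 80, shows no reversal at any visit.

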To account for repeated measures within subjects, we used a linear mixed effects model for the analysis of the primary outcome, PCL-5, with the subject treated as a random effect. We have PCL-5 measures at four times during the course of the study: at baseline, 8 weeks (the first post-treatment assessment), and 3 and 6 months post-treatment. The response (dependent) variable was PCL-5 score, and the predictor (explanatory) variables included treatment group, assessment visit (treated as categorical), and a treatment group by assessment visit interaction term, along with the covariates trauma category and rural status. A significant treatment group by visit interaction term indicates a significant difference in change from baseline between treatment groups. Results include adjusted means, standard errors, and 95% confidence intervals for each group at each time, confidence intervals for change from baseline at each time within each group, confidence intervals for differences in change from baseline between the two groups at each time, p-values, and effect sizes. We also used linear mixed effects models for the two secondary outcomes, depression and quality of life.

Linear mixed effects models easily accommodate missing values. We compared the rate and timing of dropouts between treatment groups, and also baseline demographics and outcome scores between treatment completers and non-completers. If necessary, we will perform sensitivity analyses by using only participants who were treatment completers and using multiple imputation to deal with missing values.

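### Does the 80% power figure belong to a different test from the one the analysis section interprets?

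*Combined protocol and SAP*

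**What the plan says.** Under **Power**, the plan takes up to 30% dropout from 100 randomised, leaving at least 35 per group, and states that "we have 80% power to detect an effect size of 0.68 using a two-sided Type I error rate of 5"%. The sentence names neither a test nor a visit. The paragraph before it quotes earlier results visit by visit: one trial "observed a differential effect size of 0.41 at 8 weeks", then 0.10 at 3 months and 0.95 at 6 months; in the other the first effect was 0.23, "the 12-week effect size was 0.47" and the last was 0.08. Table 1 then shows "95% confidence intervals for the difference in change from baseline in PCL-5 for the DESTRESS-WV versus the phone monitoring only group", again with no visit named.

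Under **RCT data analytic strategy**, PCL-5 is analysed by a linear mixed model "with the subject treated as a random effect". Visit is categorical (baseline, 8 weeks, 3 and 6 months post-treatment) and the model includes a group-by-visit interaction. The only sentence that interprets significance is: "A significant treatment group by visit interaction term indicates a significant difference in change from baseline between treatment groups". The listed output includes "confidence intervals for differences in change from baseline between the two groups at each time", followed by p-values and effect sizes. PCL-5 is called the primary outcome, but no test, contrast or visit is called primary.

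**The concern.** The two sections seem to describe different tests. With two groups and four categorical visits the interaction has (2 − 1)(4 − 1) = 3 degrees of freedom, while an effect size of 0.68 with 35 per arm describes one contrast. A reader could take the 80% as the power of the interaction, although that power depends on how the effect varies over visits, and both cited trials show strong variation.

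There is also a question of interpretation. The interaction and the visit-specific intervals can disagree, and the plan does not say how that would be read. If any one of three visit differences excluding zero were counted as success, the false-positive rate would exceed 5%. At stake would be the meaning of the stated power and the control of Type I error for the primary outcome.

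**Working it through.** **Inputs from the plan.** Two-sided 5%; 1:1 allocation; 100 randomised, so 50 per arm; at least 35 per arm after dropout; effect 0.68; four visits. Table 1 measures effects in units of the SD of change. The plan gives no correlation between changes at different visits. A random-subject model implies 0.5 with complete data: change at visit j is e_j − e_0, with variance 2σ² and covariance σ² between visits. A range of 0.3 to 0.7 is assumed as a check.

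**1. The plan's own figure.** Two-sample t-test, 68 df, noncentrality 0.68 × √(35/2) = 2.845, critical value 1.995: power 0.801. The effect detectable with 80% power is 0.679. Table 1 half-widths are 1.995 × SD × √(2/35), giving 3.8, 7.2 and 10.5 for SD 8, 15 and 22, as printed. Both are single-contrast calculations, and both are right.

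**2. Interaction power, 35 complete per arm.** Noncentrality λ = (35/2) d′R⁻¹d, where d holds the three visit effects and R their correlation matrix; the reference is a 3-df noncentral chi-square with critical value 7.815. At correlation 0.5 this reduces to λ = 35 × [Σd² − (Σd)²/4]. The cited shapes are rescaled so that the largest visit effect is 0.68.

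| Effect at the three follow-ups | λ at 0.5 | Power at 0.5 | Power at 0.3 / 0.7 |
|---|---|---|---|
| 0.68 throughout | 35 × (1.387 − 1.040) = 12.14 | 0.845 | 0.920 / 0.766 |
| Shape 0.41, 0.10, 0.95 (rescaled 0.293, 0.072, 0.68) | 35 × (0.554 − 0.273) = 9.82 | 0.753 | 0.696 / 0.889 |
| Shape 0.23, 0.47, 0.08 (rescaled 0.333, 0.68, 0.116) | 35 × (0.587 − 0.318) = 9.39 | 0.731 | 0.695 / 0.858 |

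The peak effect detectable with 80% power at correlation 0.5 is 0.64 (uniform) or 0.72-0.73 (cited shapes), against the stated 0.68. Unscaled, the two cited profiles give about 97% and 40%. The size of the effect therefore matters far more than the choice of test.

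**3. The planned analysis set.** Everyone randomised with a baseline is analysed, so 50 per arm contribute at baseline and, at the assumed minimum, 35 at each follow-up. For within-person correlation 0.3 / 0.5 / 0.7:

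- uniform 0.68: 0.905 / 0.888 / 0.871
- first cited shape: 0.780 / 0.771 / 0.763
- second cited shape: 0.765 / 0.754 / 0.745

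**4. Type I error.** If the interaction decides, it is 5%. If any visit interval excluding zero counted as success, simulation gives 12.5% at correlation 0.5 (13.6% at 0.3, 10.9% at 0.7). The plan states no such rule.

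**5. Disagreement.** With 35 complete per arm, peak 0.68 and correlation 0.5, the interaction result and the event that at least one visit interval excludes zero differ in 11-15% of simulated trials (6-17% over 0.3-0.7). In most of these a visit interval excludes zero while the interaction is not significant.

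**The case for a change.** The strongest case for a change is that the plan, pilot or not, states both a power and a Type I error rate and defines what a significant result means, so it should say which test these attach to. The listed p-values sharpen this, since they follow the visit contrasts and carry no decision rule. A few sentences would settle it at no cost in patients or analyses, and would remove any freedom to choose afterwards among an interaction and three visit contrasts.

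Part of this stands: the label is absent, no interaction power is given, and the role of the p-values is unstated. Three things limit its weight.

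- The 3-df reading is an inference, though the more natural one. With baseline as the reference visit, each interaction coefficient is itself the between-group difference in change at that visit, which is the contrast that was powered.
- The end-of-study dropout figure makes 35 per arm a minimum at every follow-up if those who drop out do not return, so the 80% holds whichever visit is meant.
- Much of the analysis section is in the past tense. Declaring any test primary now, the interaction included, could be a post hoc choice if outcome data had been seen, and would then need that label.

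**Conclusion.** No change to the plan follows. The stated 80% is correct for the single between-group difference that the Power section and Table 1 describe. The analysis section, followed as written, yields a 5% test of the interaction with visit-by-visit estimates that show timing and direction. The 12.5% error rate belongs to a rule the plan does not contain.

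The difference between the two power figures is modest and has no consistent direction. On the planned analysis set, interaction power is about 87-91% for a uniform 0.68 and about 75-78% for the cited shapes rescaled to a 0.68 peak. This assumes a random-subject model, 35 per arm at each follow-up and within-person correlation from 0.3 to 0.7. The cited shapes illustrate variation only: the 0.95 rests on 18 participants, and the second trial's visits (6, 12 and 18 weeks) are not this trial's.

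The plan presents the trial as a pilot for feasibility, dropout, acceptability and initial effect sizes, with its size set by budget and timeline. In that setting the missing label is a gap that a competent analyst fills sensibly: the interaction is the test, the visit differences are estimates, and the 80% refers to one visit.

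### The primary PCL-5 model names only a subject random effect; read plainly this is a random intercept, which can miscalibrate the between-arm intervals and p-values promised at each visit

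*Combined protocol and SAP*

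**What the plan says.** The section on the RCT data analytic strategy states: "we used a linear mixed effects model for the analysis of the primary outcome, PCL-5, with the subject treated as a random effect". PCL-5 is measured "at baseline, 8 weeks (the first post-treatment assessment), and 3 and 6 months post-treatment". The fixed effects are group, categorical visit, their interaction, trauma category and rural status. The promised output includes "confidence intervals for differences in change from baseline between the two groups at each time, p-values, and effect sizes". One test is given an interpretation: "A significant treatment group by visit interaction term indicates a significant difference in change from baseline between treatment groups". For PHQ-8 and Q-LES-Q-SF the text is shorter still: "We also used linear mixed effects models for the two secondary outcomes, depression and quality of life".

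The documents name no random slope, residual covariance structure, robust variance, degrees-of-freedom method or fallback. The two sensitivity analyses, to be run if needed, are a completers-only analysis and multiple imputation. Neither concerns the covariance.

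The Power section calls the trial a pilot "designed to provide estimates of feasibility of the treatment approach, dropout rates, acceptability, and initial effect sizes". It says that budget and timeline allow 100 women to be randomized. It then gives 80% power for an effect size of 0.68 at 35 per group, two-sided 5%. Table 1 lists "95% confidence intervals for the difference in change from baseline in PCL-5 for the DESTRESS-WV versus the phone monitoring only group" for a range of SDs of change. Neither names a visit.

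**The concern.** A random intercept with homogeneous residuals assumes that any two visits are equally correlated and that all visits have the same variance. The variance of change from baseline is then the same at 8 weeks, 3 months and 6 months, and the per-visit standard errors differ only through the numbers observed. The visits fall at about 0, 2, 5 and 8 months, with treatment between the first two, so equal correlation cannot be taken for granted.

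If it fails, the model averages over visits. It reports too small a standard error where change is more variable than average and too large a one where it is less variable. What is at stake is the width of the between-arm intervals and the p-values at individual visits, in a pilot that names initial effect sizes among its products.

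**Working it through.** **1. The plan's own figures.** A two-sample t-test with 35 per arm, d = 0.68 and two-sided 5% has 80.1% power, against the stated 80%. The Table 1 half-width for SD 15 is t(68) × SD × √(2/35) = 1.995 × 15 × 0.239 = 7.2, as printed. All nine intervals reproduce. The plan's arithmetic is sound, and both calculations are generic two-group comparisons.

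**2. Inputs.** From the documents: four visits, 1:1 allocation, 100 randomized, 35 per arm at the end. Assumed, because the documents give none: between-visit correlations and visit SDs. Each pattern below lists the three correlations with baseline, then those between follow-ups (8 weeks-3 months, 8 weeks-6 months, 3-6 months).

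**3. Formula (complete data, equal SDs σ, n per arm).**
- The random-intercept residual variance estimates s² = σ²(1 − ρ̄), with ρ̄ the mean of the six correlations.
- Model variance of the between-arm difference in change: 4s²/n at every visit.
- True variance: (2/n) × Var(Y_t − Y_0) = (4σ²/n)(1 − ρ_0t).
- Ratio R = (1 − ρ_0t)/(1 − ρ̄). Large-sample type I error = 2[1 − Φ(1.96/√R)].

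Example, the moderate pattern (.55/.50/.45; .75/.65/.75): ρ̄ = 3.65/6 = .608. At 6 months R = .55/.392 = 1.40 and √R = 1.185, so 1.96/1.185 = 1.654 and the error is 9.8%.

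**4. Results.** Type I error in % at 8 weeks / 3 months / 6 months, random intercept, equal SDs:

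| Assumed correlations | Complete data, formula | 45/40/35 per arm observed |
|---|---|---|
| Equal, .6 | 5.0 / 5.0 / 5.0 | 4.8 / 5.0 / 5.1 |
| Mild: .65/.60/.55; .70/.65/.70 | 4.7 / 6.4 / 8.0 | 4.7 / 6.1 / 7.5* |
| Mild: .55/.55/.50; .65/.60/.65 | 5.9 / 5.9 / 7.4 | 5.7 / 5.6 / 6.8* |
| .5 with baseline, .7 between follow-ups | 8.0 / 8.0 / 8.0 | 7.6 / 7.3 / 7.0 |
| Moderate: .55/.50/.45; .75/.65/.75 | 6.7 / 8.3 / 9.8 | 6.5 / 7.7 / 9.0 |
| .4 with baseline, .8 between follow-ups | 11.0 / 11.0 / 11.0 | 10.2 / 9.6 / 9.1 |
| Autoregressive, .8 per visit | 1.6 / 7.3 / 12.4 | 1.8 / 7.5 / 12.5 |
| Autoregressive, .9 per month | not computed | 0.8 / 6.9 / 12.3 |

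The last column comes from 40,000 simulated null trials per pattern (50 per arm, dropout completely at random, REML), except the rows marked *, which are large-sample values. If only the SDs rise (12/15/16/17, correlation .6), the simulated errors are 3.2 / 4.7 / 6.2.

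**5. Group-by-visit test.** Across six simulated patterns with unequal correlations and equal SDs (the four in the table and a Toeplitz-shaped .7/.6/.5, plus .9 per month counted among the autoregressive rows), the error is 5.2-7.2%.

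**6. Alternatives.** Over ten simulated patterns, including unequal SDs, an unstructured covariance gives 4.8-5.3% per visit and 5.1-5.3% for the interaction. Observed n minus 2 degrees of freedom stood in for Kenward-Roger. A random intercept with a Kauermann-Carroll corrected sandwich and the same degrees of freedom gives 4.8-5.2% and 4.8-5.0%. The uncorrected sandwich with a normal reference gives 5.4-5.9% per visit. A heterogeneous Toeplitz fit (large-sample) gives 8.5 / 5.9 / 4.8 under the moderate pattern and 11.3 / 7.6 / 4.4 under .4/.8.

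**7. On the PCL-5 scale.** With an assumed score SD of 15, going from random intercept to unstructured moves the 6-month standard error from 3.04 to 3.47 under the moderate pattern (3.04/3.47 = 0.88, an interval about 12% too narrow). Under .9 per month the 8-week value falls from 2.62 to 1.94. Under equal correlation nothing changes.

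**The case against.** The strongest reply is that silence is being read as a choice. The text does not say that residuals are independent, and the analysts may have used another structure or robust errors. That stands: the documents establish what the stated model means on its plain reading, not what was run.

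All harm also depends on assumed correlations. That stands too. The largest errors need autoregressive patterns with a baseline-to-8-week correlation of about .8, across the interval in which treatment is given. The only correlation-type figure in the documents is the PCL-5 test-retest value of .84, given without an interval, and it does not settle the matter. The mild-to-moderate rows are therefore the fair summary, and some error at 6 months remains in all of them.

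The one test that the plan interprets, group by visit, is nearly unaffected, and no decision rule is attached to single visits. Correct, but intervals and p-values at each time are promised, and those are the exposed part.

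A reader might infer that the trial was sized on a per-visit contrast, so that its power is now in doubt. The documents do not support this. The size follows budget and timeline, no visit is named in the power statement or Table 1, and both reproduce unchanged.

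Pilot status lowers the stakes, but it does not remove the interest in well-calibrated intervals around the effect sizes.

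**Conclusion.** The point holds as a calibration weakness, not as a proven error. On its plain reading the model ties the three per-visit standard errors to one variance of change. Under assumed mild-to-moderate unequal correlations the per-visit type I error is about 5-8% at 8 weeks and 7-10% at 6 months. Stronger assumed patterns span about 1% to 12.5%, and equal correlation with equal SDs gives 5%. Which visit suffers most depends on the pattern: 6 months if correlation decays with time, all three about equally if the follow-ups correlate more with each other than with baseline.

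A reader might infer that the reported intervals are wrong, or that they err in a known direction. Neither can be read from the documents, which give no correlations or visit SDs and do not confirm the structure used. Complete-data point estimates are unaffected. Nothing is claimed here about within-arm intervals or bias from dropout. The change is worth making because it is cheap and removes reliance on an unstated assumption.

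**What to change.** State in the data analytic strategy: PCL-5, PHQ-8 and Q-LES-Q-SF at the four visits are each modelled with an unstructured covariance common to both arms, fitted by REML with Kenward-Roger degrees of freedom. If this does not converge, the random intercept is kept with subject-level sandwich standard errors, the Kauermann-Carroll correction and observed n minus 2 degrees of freedom. A Toeplitz structure should not be the fallback: it cannot let baseline correlate differently from the follow-ups, and it ignores the unequal spacing.

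The section is largely in the past tense. If the analysis is done, report the structure that was used and, if it was a random intercept, add the unstructured fit as a labelled sensitivity analysis.

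Cost: one or two sentences, or a re-run with disclosure. There are ten covariance parameters instead of two, with some convergence risk at 35-50 women per arm. Some per-visit intervals may widen.
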